2.2.2. Secondary Endpoints

Secondary endpoints of this study are:

- DSA levels up to 180 days after treatment
- HLA-antibodies levels up to 180 days after treatment
- Kidney function change from baseline (at screening) as evaluated by eGFR, P-creatinine and albumin/creatinine ratio in urine up to 180 days after treatment
- Proportion of subjects with graft loss within 180 days of treatment
- Signs of transplant glomerulopathy 180 days post treatment
- Change from baseline (at screening) in histopathology per Banff Criteria at 29 and 180 days

- Change from baseline (at screening) in mRNA levels in kidney biopsies evaluated by [REDACTED] at 29 and 180 days from baseline. If kidney biopsy is performed before screening, mRNA levels will be evaluated on day 29 and day 180 (no baseline will be available)
- Safety parameters (AEs, safety laboratory tests, vital signs and ECG)
- Type, frequency and intensity of adverse events
- Number of sessions with PE
- Total Serum IgG levels over time
- Presence of intact IgG on SDS-page/Western blot until start of IVIg treatment
- DSA functionality determined by C1q or C3d analysis pre- and post-treatment
- PK profile of imlifidase (C_{max} , T_{max} , $t_{1/2}$, AUC, CL, V)
- Presence of ADA (anti-imlifidase IgG)

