3.1.1. Follow-up Procedures

The subjects will be followed until 180 days after start of treatment. Subjects who lose their graft during the course of the study will remain in the study and be followed according to the study protocol and clinical practice at the site.

After study completion, all study subjects will be followed regularly by the nephrologist or transplant surgeons according to each centre's follow-up routines for transplanted subjects. The frequency of outpatient visits will be adjusted individually to the state of patient health and transplant function.

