4.2. Inclusion Criteria

1. Signed Informed Consent obtained before any study-related procedures
2. Willingness and ability to comply with the protocol
3. Male and/or female donor kidney recipients age ≥ 18 years at the time of screening
4. Presence of DSA(s)
5. Meet the Banff 2017 criteria for active or chronic active AMR
6. At least 25% rise in serum creatinine compared to last individual value taken prior to the AMR. Patients with delayed graft function and AMR within 10 days after transplant (confirmed by kidney biopsy) can be included regardless of serum creatinine level
7. Women of child-bearing potential willing or able to use at least one highly effective contraceptive method throughout the study. In the context of this study, an effective method is defined as those which result in low failure rate (i.e. less than 1% per year) when used consistently and correctly such as:
 - combined (estrogen and progestogen containing) hormonal contraception associated with inhibition of ovulation
 - oral
 - intravaginal
 - transdermal
 - progestogen-only hormonal contraception associated with inhibition of ovulation
 - oral
 - injectable
 - implantable
 - intrauterine device (IUD)
 - intrauterine hormone-releasing system (IUS)
 - bilateral tubal occlusion
 - vasectomised partner
 - true abstinence: When this is in line with the preferred and usual lifestyle of the subject. [Periodic abstinence (such as calendar, ovulation, symptothermal, post-ovulation methods) and withdrawal are not acceptable methods of contraception]
8. Men willing to use double-barrier contraception from the first day of treatment until at least 2 months after the dose of imlifidase, if not abstinent

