6.1.10. Visit 11 (follow up, end of study), day 180 (+/- 14 days)

The following activities and assessments will be performed:

- Physical examination
- Blood pressure, pulse rate and body temperature will be monitored
- Safety laboratory tests (Table 5) will be collected
- ECG
- Pregnancy test (serum)
- Urine sample for measurement of albumin/creatinine ratio
- Kidney biopsy will be performed
- Samples for DSA, PD and ADA (IgG) will be collected

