12.3.7. Number of sessions with PE for 180 days

The number of PE sessions for 180 days will be summarized by treatment and listed.

12.3.8. Number of patients with resolution of AMR at day 180

The number of patients with resolution of AMR at day 180 will be tabulated by treatment and listed.

12.3.9. The number of patients with graft failure at day 180

The number of patients with graft failure at day 180 will be summarized by treatment and listed.

12.3.10. Patient survival at day 180

The patient survival on day 180 will be tabulated and listed.

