1.1.2 Endpoints

The primary endpoint of this study is:

- Maximum reduction in DSA level at any time point during the 5 days following the start of treatment

The secondary endpoints of this study are:

- DSA levels up to 180 days after treatment
- HLA-antibodies levels up to 180 days after treatment
- Kidney function change from baseline (at screening) as evaluated by estimated Glomerular Filtration Rate (eGFR), P-creatinine and albumin/creatinine ratio in urine up to 180 days after treatment

- Proportion of patients with graft loss within 180 days of treatment
- Signs of transplant glomerulopathy 180 days post treatment
- Change from baseline (at screening) in histopathology per Banff Criteria at 29 and 180 days
- Change from baseline (at screening) in mRNA levels in kidney biopsies evaluated by [REDACTED] [REDACTED] at 29 and 180 days from baseline. If kidney biopsy is performed before screening, mRNA levels will be evaluated on day 29 and day 180 (no baseline will be available)
- Safety parameters (adverse events [AEs], safety laboratory tests, vital signs and electrocardiogram [ECG])
- Type, frequency and intensity of adverse events
- Number of sessions with PE
- Total Serum Immunoglobulin G (IgG) levels over time
- Presence of intact IgG on SDS-page until start of IVIg treatment
- DSA functionality determined by C1q or C3d analysis pre- and post-treatment
- PK profile of imlifidase (C_{max} , T_{max} , $t_{1/2}$, AUC, CL, V_z)
- Presence of anti-implifidase IgG (ADA)
- Number of patients with resolution of AMR at day 180
- Patient survival at day 180

2 Study design

The study is a phase II, randomized, open-label, multi-centre study with an active control investigating the efficacy and safety of imlifidase compared with PE, in removing anti-HLA antibodies to treat active and chronic active AMR post-transplant. A total of 30 male and/or female patients will be included in the study. The 30 patients are planned to be distributed in 5 countries (France, Austria, US, Australia and Germany) and 14 sites.

DSA measurements and biopsies will be done at screening. If deemed eligible for the study during the screening visit, patients will be randomized in ratio 2:1 in the following way:

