4.6.2 Secondary efficacy analyses

DSA levels up to 180 days after treatment

DSAs will be measured using SAB-HLA assay and a functional assay e.g. C1q or C3d assay. A summary table for the C1q assay will be generated for the sum of MFI levels for DSAs from step 1 for primary endpoint (see Section 4.6.1) by treatment and time point. MFI levels will be listed per patient and time point. Spaghetti plots will show the DSA level versus time for each patient. A mean plot by treatment and time point will be presented.

A list with all DSA by patient and time point will be presented.

HLA-antibodies levels up to 180 days after treatment

Patient listings of MFI values for all HLAs will be presented.

Kidney function change from baseline

The kidney function will be evaluated by the parameters eGFR, P-creatinine and albumin/creatinine ratio in urine. The laboratory parameters will be summarised as part of the safety data tabulation.

The eGFR will be calculated as a part of ADaM programming, using the Modification of Diet in Renal Disease Study (MDRD) equation (2):

$$\text{eGFR (mL/min/1.73 m}^2\text{)} = 175 \times (\text{Cr})^{-1.154} \times (\text{Age})^{-0.203} \times (0.742 \text{ if female}) \times (1.212 \text{ if African American}),$$

where Cr stands for creatinine value and Age are measured in years from birth to screening visit. This formula assumes that Cr is given in the mg/dL unit.

Proportion of patients with graft loss at day 180

The number of patients with graft loss at day 180 will be handled as a binary variable. Graft loss is defined as permanent return to dialysis for at least 6 weeks, re-transplantation, or transplantectomy. The endpoint is a success if the patients have absence of graft loss at day 180. The proportion of patients, which satisfy the success criterium, will be summarized by treatment and listed by patient. The FAS set will be applied.

Signs of transplant glomerulopathy 180 days post treatment

Possible transplant glomerulopathy 180 days post treatment will be handled as a binary variable. The endpoint is a success if the patients have no possible transplant glomerulopathy 180 days post treatment. The proportion of patients, which satisfy the success criterium, will be tabulated by treatment. A list will also be created by patient. The FAS set will be applied.

Change from baseline in histopathology per Banff Criteria at 29 and 180 days

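### Graft loss by dialysis needs 6 weeks on dialysis but is judged at Day 180, so permanent dialysis starting after about Day 138 is, read literally, scored as a success

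*SAP*

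**What the plan says.** Protocol 2.2.2 lists the secondary endpoint as "Proportion of subjects with graft loss within 180 days of treatment", and SAP 1.1.2 repeats it as "Proportion of patients with graft loss within 180 days of treatment". Protocol 12.3.9 gives the analysis in one line: "The number of patients with graft failure at day 180 will be summarized by treatment and listed". The protocol does not define graft loss or graft failure.

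The definition appears only in SAP 4.6.2: "Graft loss is defined as permanent return to dialysis for at least 6 weeks, re-transplantation, or transplantectomy". The same paragraph makes the variable binary: "The endpoint is a success if the patients have absence of graft loss at day 180".

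On follow-up, Protocol 3.1.1 says "The subjects will be followed until 180 days after start of treatment". The last visit in Protocol 6.1.10 is "Visit 11 (follow up, end of study), day 180 (+/- 14 days").

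On eligibility, Protocol 4.2 states: "Patients with delayed graft function and AMR within 10 days after transplant (confirmed by kidney biopsy) can be included regardless of serum creatinine level".

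SAP section 5, which records departures from the protocol analysis, does not mention this endpoint.

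**The concern.** The definition and the time of judgement do not fit together. Of the three routes to graft loss, only dialysis carries a minimum duration, and that duration has to be completed inside a follow-up period that stops at Day 180. A patient who goes onto dialysis for good near the end of the study has lost the graft within 180 days in any ordinary sense. That patient has not yet met the SAP's definition, and under the binary rule anyone who has not met it is a success.

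The SAP does not say whether a dialysis-defined loss is dated at the start of dialysis or when 6 weeks are complete. It does not say how dialysis of under 6 weeks at the last visit is classified, or whether status is confirmed after Day 180.

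There is a second, separate gap. The definition speaks of a *return* to dialysis, while patients with delayed graft function are eligible. If such a patient is on dialysis at entry and never comes off it, the 6-week duration is met but nothing has been returned to. The variable needs one answer, and the SAP gives none.

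With arms of 20 and 10, a single classification visibly changes the reported proportion. SAP 2.3 describes the study as fully unblinded, so a rule left unwritten would be settled with the treatment arm known.

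**Working it through.** The documents give no expected rate, precision or sample size for graft loss, so there is no plan figure to reproduce. The check is a calendar calculation.

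**Inputs**
- Minimum dialysis duration: 6 weeks = 6 × 7 = 42 days (SAP 4.6.2).
- Time of judgement: Day 180 (SAP 4.6.2).
- Last visit: Day 180 ± 14, so Day 166 to Day 194 (Protocol 6.1.10).
- Arm sizes: 20 imlifidase, 10 PE (Protocol 12.4; SAP 2.2).

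**Step 1. Latest dialysis start that can complete 6 weeks**

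Latest start = day of judgement − 42.

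| Status read on | Latest start |
|---|---|
| Day 166 (earliest last visit) | 166 − 42 = Day 124 |
| Day 180 | 180 − 42 = Day 138 |
| Day 194 (latest last visit) | 194 − 42 = Day 152 |

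Counting both end days as dialysis days moves each figure one day later (Day 139 in the central case).

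**Step 2. A worked case**

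Permanent dialysis starts on Day 150 and is ongoing at Day 180: 180 − 150 = 30 days, which is under 42. With no re-transplantation or transplantectomy, none of the three routes is met, and the success rule applies.

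**Step 3. Share of follow-up affected**

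42 / 180 = 23.3%. This is the share of follow-up time in which a dialysis start cannot become a dialysis-defined loss by Day 180. It would equal the share of dialysis-defined losses only under a constant failure rate, and the documents give no time pattern.

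**Step 4. Effect of one patient**

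Imlifidase: 1/20 = 5 percentage points. PE: 1/10 = 10 percentage points.

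**Step 5. Does another passage resolve it?**
- SAP 4.1.4 leaves missing data as missing. Its exceptions concern adverse events and dates, not dialysis status.
- Protocol 9.2.4 provides for following unresolved adverse events after the last assessment, but neither document links this to the graft-loss endpoint.
- Protocol 3.1.1 keeps patients who lose the graft in the study, but only to Day 180.

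None of these says how dialysis of under 6 weeks at the last visit is classified.

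**The case against.** The strongest defence is that scoring these patients as successes is one reading and not an explicit instruction. The endpoint is loss within 180 days, and a permanent return to dialysis inherently needs later confirmation. The loss could therefore be dated at dialysis start, with the 6 weeks serving only to confirm permanence. A late return to dialysis reported as an adverse event could be followed past the last visit under Protocol 9.2.4. It would also be visible in the SAE or post-treatment AE listings (SAP section 8). The analysis is descriptive, with no test and no confidence interval for this endpoint.

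Much of that stands as a limit on importance. It does not remove the problem, because the SAP does not state the favourable reading, and the rule as written sends these patients to success.

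A reader might also infer four stronger things that the documents do not support:

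- *Every graft failing after about Day 138 is scored as a success.* Re-transplantation and transplantectomy have no minimum duration and still count after that day.
- *About 23% of losses are missed.* The figure is a share of follow-up time (Step 3).
- *A delayed-graft-function patient who never leaves dialysis is definitely scored as a success.* No passage says such patients are on dialysis at entry, and only a literal reading of *return* excludes one who is. A programmer could code the case either way.
- *The rule hides late losses caused by antibody rebound, and so favours imlifidase.* The documents do not say that losses cluster late. Protocol 1.3 and 3.1 expect rebound to be detected early and treated, and the rule is the same in both arms.

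**Conclusion.** The point holds for the dialysis route. Applied as written, SAP 4.6.2 scores as a success a patient whose permanent dialysis starts after about Day 138 and who has neither re-transplantation nor transplantectomy. This contradicts an endpoint defined as loss within 180 days. The cut-off assumes status is read on Day 180; reading it at the last visit instead moves it within Day 124 to 152. The number of patients affected cannot be estimated from the documents and may be none, but each one shifts an arm by 5 or 10 points.

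The delayed-graft-function case is an ambiguity that needs a stated answer, not a demonstrated misclassification.

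The endpoint is secondary and descriptive, and the primary endpoint is unaffected. The change should be made, but the main result of the trial does not depend on it.

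**What to change.** In SAP 4.6.2:

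1. Date a dialysis-defined loss at the start of dialysis.
2. Count as lost any patient whose dialysis for graft failure started on or before Day 180 and is ongoing at the last visit. Name patients continuously dialysis-dependent from entry as included.
3. Use the 6-week rule only to exclude temporary dialysis that has already stopped.
4. Leave re-transplantation and transplantectomy as they are.
5. Flag patients with under 6 weeks of dialysis at the last visit, and add one sensitivity row to the graft-loss table (14.2.6) counting them as not lost.

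The cost is SAP wording, one flag and one table row. Protocol 5.7 already has other therapy recorded with start and stop dates from screening to end of study, and Protocol 7.3.3 repeats that other treatments are recorded throughout. Neither names dialysis, so the sponsor should confirm that the eCRF captures its dates.

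The downside is small: temporary dialysis that happens to be ongoing at Day 180 may be counted as a loss. The sensitivity row shows how much that matters.

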12.3.2. Reduction of total serum IgG

The total serum IgG is measured by the PD assay. A binary endpoint is defined as 'Yes' if the subject minimum IgG value at any timepoint during the 5 days following the start of treatment is less than 5% of baseline. The proportion of subjects with a positive reduction will be summarized in a table. The difference in proportion between treatments will be presented with a 95% CI.

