12.4. Determination of Sample Size

Due to the exploratory nature of the study, there is no formal statistical hypothesis. The difference between treatments for the reduction of DSA will however be presented with 95% confidence interval. A sample size of 20 implifidase and 10 PE subjects is proposed.

In two previous implifidase studies, 14-HMedIdeS-04 and 15-HMedIdeS-06, the IgG reduction for 5 days was 90% and 93% respectively. The corresponding standard deviations are 6% and 4% respectively. Assuming a similar variability in the PE treatment arm, the expected width of the 95% CI for the difference in DSA reduction will be around 8% point. This supports that 20+10 patients are appropriate. Also, the sample size is in line with experience from previous similar Phase II studies with other compounds to obtain adequate safety, tolerability and PK data to achieve the objectives of the study.

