2.2 Determination of sample size

No formal calculation has been done for the sample size. A sample size of totally 30 patients is chosen where 20 patients are treated with imlifidase and 10 patients are treated with PE.

The standard deviations for the two previous studies 14-HMedIdeS-04 and 15-HMedIdeS-06 can be considered to argue for the sample size of 30 patients. The standard deviations for the reduction of the IgG were 6% in the 14-HMedIdeS-04 and 4% in the 15-HMedIdeS-06 study. If the standard deviations are assumed to be similar in this study, it will give approximately an 8% point wide Confidence Interval (CI) when the sample size on 10+20 patients are considered. The 8% point wide of the CI is an acceptable wide and therefore the sample size on 30 patients can be used.

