4.1.1 Data presentation

No formal statistical hypothesis testing will be performed in this study.

The data will be presented descriptive and for some of the endpoints 95% confidence intervals for the treatment difference will be presented.

Numerical data will be presented in summary tables by number of patients, arithmetic mean, median, standard deviation (SD), minimum and maximum.

When numerical data are recorded at different time points, absolute values at each time point and changes from baseline may be presented in the summary tables.

Categorical data will be presented by frequency and percent of patients. Number of events will also be reported where applicable.

Summary tables will in general be presented by treatment group and total across treatment groups unless this is not appropriate for specific tables.

Data will be listed by treatment group, patient and time point (if applicable).

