In addition, the reduction of total serum IgG levels will be analyzed as a binary endpoint. The binary endpoint is defined as a success, if the minimum IgG value at any time point during the 5 days following the start of treatment is less than 5% of baseline for the patient. The proportion of patients, which satisfy the success criterium, will be presented in a summary table by treatment. The difference in proportion between the two treatments will be presented with a 95% CI in a summary table. The 95% CI for the difference between the two treatments will be based on exact Confidence Limits. In addition, the proportion of patients which satisfy the success criterium will be presented by treatment and time point.

The composition of IgG-fragments will be analyzed centrally using SDS-PAGE. Each sample will be assigned a score depending on the observed composition of fragments as follows:

- 0=no intact IgG, scIgG or F(ab')₂
- 1=only F(ab')₂
- 2=mix of scIgG and F(ab')₂
- 3=only scIgG
- 4=mix of intact IgG and scIgG
- 5=only intact IgG

SDS-PAGE scores will be summarized by time point.

Presence of intact IgG on SDS-PAGE until start of IVIg treatment

The endpoint is a success for a patient if no detectable intact IgG is found by the SDS-PAGE assay for at least one time point between the start of study medication (imlifidase) treatment and start of administration of IVIg. No detectable intact IgG is defined as SDS-PAGE scores 0, 1, 2 or 3. The

proportion of patients, who reached the success criterium, will be summarized in a table using the PKS set.

Number of patients with resolution of AMR at day 180

The number of patients with resolution of AMR at day 180 will be handled as a binary variable. Resolution is defined as “Active AMR” or “Chronic active AMR” not being selected from the biopsy protocol.

The endpoint is a success if the patients have resolution of AMR at day 180. The proportion of patients, which satisfy the success criterium, will be tabulated by treatment. A list will be created by patient. The FAS set will be applied.

Patient survival at day 180

The patient survival on day 180 will be handled as a binary variable.

The endpoint is a success if the patients have survived on day 180. The proportion of patients, which satisfy the success criterium, will be summarized and listed by patient. The FAS set will be applied.

Pharmacokinetic

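### The only treatment difference planned for total IgG is on a dichotomy (<5% of baseline) whose cut-off lies beyond both planning means; a continuous contrast should be added

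*SAP*

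**What the plan says.** SAP 4.6.2 (total serum IgG over time) plans summaries by time point, mean and spaghetti plots, and listings. It then adds a binary endpoint, met "if the minimum IgG value at any time point during the 5 days following the start of treatment is less than 5% of baseline". On the interval it says: "The 95% CI for the difference between the two treatments will be based on exact Confidence Limits". Protocol 12.3.2 sets the same cut-off and states: "The difference in proportion between treatments will be presented with a 95% CI".

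Protocol 12.4 gives the only numerical planning information on IgG. In two earlier imlifidase studies "the IgG reduction for 5 days was 90% and 93% respectively", and "The corresponding standard deviations are 6% and 4% respectively". From these SDs, and "Assuming a similar variability in the PE treatment arm", it derives a CI about 8 points wide for the primary donor-specific antibody (DSA) contrast. SAP 2.2 repeats the argument for a trial in which "20 patients are treated with imlifidase and 10 patients are treated with PE".

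SAP 4.6.1 analyses DSA as each patient's maximum percent reduction within 5 days, with a treatment difference and 95% CI from an ANOVA. SAP section 5 drops the protocol's between-arm contrast for intact IgG. SAP 4.1.1 states: "No formal statistical hypothesis testing will be performed in this study".

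**The concern.** A minimum below 5% of baseline means a reduction above 95%. Both earlier imlifidase means lie under that line, by (95 − 90)/6 = 0.83 SD and (95 − 93)/4 = 0.50 SD. Neither document explains why 5% was chosen or gives an expected success rate for either arm.

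Total IgG is the direct pharmacodynamic readout of an IgG-cleaving enzyme. With the intact-IgG contrast dropped, the <5% proportion is the one IgG result that will carry a between-arm CI. At stake is how that result reads: imlifidase could miss the criterion in most patients, with a wide interval for the difference, while removing 90% or more of IgG on average. The continuous percent reduction, whose SDs support the sample size, gets no treatment difference at all.

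**Working it through.** **Inputs.** Cut-off: reduction >95% (Protocol 12.3.2, SAP 4.6.2). Means and SDs: 90% and 6; 93% and 4 (Protocol 12.4). Patients: 20 imlifidase, 10 PE (SAP 2.2). Assumptions made here: the quoted figures are per-patient peak reductions, and 0 of 10 PE patients succeed. The documents give no PE figure for IgG.

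**1. The plan's own figure.** Full CI width = 2 × t(0.975, 28) × SD × √(1/20 + 1/10), with t = 2.048 and √0.15 = 0.3873.
- SD 5: 2 × 2.048 × 5 × 0.3873 = 7.9 points
- SD 4: 6.3 points; SD 6: 9.5 points

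The stated width of about 8 points is reproduced. It applies to a continuous percent reduction.

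**2. Expected success with imlifidase, figures read as peaks.**
- 90/6: normal 1 − Φ(0.83) = 0.20; beta 0.21, gamma 0.21, lognormal residual 0.17
- 93/4: normal 1 − Φ(0.50) = 0.31; beta 0.36, gamma 0.36, lognormal residual 0.36

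That is about 3-4 or 6-7 of 20 patients.

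**3. Exact 95% CI for the difference against 0/10.** The SAP does not name the exact method, so two unconditional versions are shown (limits searched in steps of 0.02).

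| Imlifidase | Score-based | Raw difference |
|---|---|---|
| 4/20 | −12 to +44 (width 56) | −20 to +56 (width 76) |
| 6/20 | −4 to +54 (width 58) | −10 to +64 (width 74) |
| 7/20 | +2 to +58 (width 56) | −4 to +68 (width 72) |
| 9/20 | +10 to +68 (width 58) | +6 to +76 (width 70) |

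Zero is excluded from 7/20 upward with the score version. With the raw difference, 8/20 has a lower limit at 0, so 9/20 is counted. The binomial chance of reaching those counts is:

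| True success rate | Score (≥7/20) | Raw difference (≥9/20) |
|---|---|---|
| 0.20 | 9% | 1% |
| 0.31 | 43% | 13% |
| 0.36 | 62% | 27% |
| 0.50 | 94% | 75% |

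**4. If the quoted figures are not peaks.** Shift the means up and keep the SDs, under the normal model:
- +2 points: 1 − Φ(3/6) = 31% and 1 − Φ(0) = 50%
- +3 points: 37% and 60%
- +5 points: 1 − Φ(0) = 50% and 1 − Φ(−3/4) = 77%

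The normal model is crude at the top: mean 98 and SD 4 puts 1 − Φ(2/4) = 31% of patients above 100%. A bounded beta with the same moments gives 66% and 87% at +5, which only strengthens the contrast.

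**5. Continuous contrast.** With equal SDs of 4 to 6, the CI is 6.3 to 9.5 points wide (step 1). If the PE SD were 15 and the imlifidase SD 5 (an assumption), SE = √(25/20 + 225/10) = 4.87, Welch df = 10.0, t = 2.228, and the width is 2 × 2.228 × 4.87 = 22 points. That is still far narrower relative to the 0-100 scale than 56-76 points, although a difference in means and a difference in proportions are not the same quantity.

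**The case against.** Three stronger readings are tempting, and the documents support none of them.

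*That this is the only comparison of IgG between arms.* It is not. Continuous total IgG is tabulated and plotted by time point, and SAP 4.1.1 makes tables by treatment group the default. P-IgG is also a safety laboratory test (Protocol Table 5), summarised by treatment and time point with change from baseline (SAP 4.7.2). What is true is narrower: no other IgG output carries a treatment difference with a CI.

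*That the protocol's own figures predict that most imlifidase patients will miss the cut-off.* Protocol 12.4 does not say whether 90% and 93% are peaks, averages or values at one time. The endpoint takes the best of several samples (2 to 96 hours in the visit 2 flow chart), and a patient's best value cannot be below that patient's average. Protocol 1.1 also describes the whole IgG pool as cleaved within hours. Mean and SD alone do not force a majority to miss: the one-sided Chebyshev upper bounds on success are 36/(36 + 25) = 59% and 16/(16 + 4) = 80%. In favour of the peak reading, 12.4 uses these SDs to plan a contrast of 5-day maxima. That makes the reading plausible but does not establish it.

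*That the binary contrast is close to uninformative.* This needs both the lower success rates and a PE rate near 0. No PE session frequency or IgG response is given, and immunoadsorption may replace PE. At a true rate of 50% or more the interval would usually exclude zero. Nothing is tested, so an interval that includes zero is imprecise rather than a failed test.

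It is also fair to say that the cut-off was pre-specified, that it asks a legitimate question about near-complete removal, and that SDS-PAGE scores read cleavage separately. All of this stands. None of it supplies a continuous treatment difference.

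**Conclusion.** The point holds as a loss of information, not as an error of inference. SAP 4.6.2 estimates the between-arm IgG difference only after dichotomising a continuous measure, at a cut-off above both means quoted in Protocol 12.4.

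Its size depends on what those means measure. Read as peaks, about 20-36% of imlifidase patients would succeed (17% at the lowest, under one shape), and the exact CI against an assumed 0/10 would span roughly 56-76 points. It would include zero with a chance between 38% and 99%, depending on the true rate and the exact method. With peaks 5 points higher, success is about 50-77% and the contrast is usually clear.

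Under either reading a continuous contrast is the more precise summary: 6 to 10 points wide if the PE SD matches the imlifidase SD, which the protocol only assumes, and about 22 points if the PE SD were 15. Because the endpoint is secondary and descriptive, this is a cheap improvement worth making; the primary analysis is not affected.

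**What to change.** In SAP 4.6.2, add the per-patient maximum percent reduction in total serum IgG within 5 days of the start of treatment. Present the treatment difference with a 95% CI by the method used for the primary DSA endpoint, but allow unequal variances, because the PE SD is only assumed to be similar. Keep the protocol-defined <5% proportion and its exact CI beside it, and name the exact method, since at 7/20 against 0/10 the two versions fall on different sides of zero. No further cut-off is needed. A sentence stating what the 90% and 93% in Protocol 12.4 measure would let readers judge the 5% cut-off.

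The cost is SAP wording and one table from data already collected. The downside is one more CI in a descriptive study.
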